8.5 Biochemistry, Hematology and Urinalysis

All analyses of laboratory data will be based on the planned visits. Laboratory data collected at unscheduled visits will be available in the data listings but not included in summary tables.

Descriptive statistics for each clinical laboratory test will be presented for each scheduled visit. Change from baseline to each follow-up assessment will be also presented. According to the laboratory normal ranges, laboratory test results will be categorized as low (< lower normal limit), normal (within normal range), and high (> upper normal limit). Shift tables comparing the distributions of these three categories at baseline versus end of treatment will be presented.

Urinalysis assessments will consist of pH, specific gravity, ketones, blood, glucose, and protein. The raw data listings for each individual patient will be produced for further evaluation, whenever needed.

Clinically significant laboratory values will be reported as AEs.

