## 5.4 Weekly or Biweekly Assessments

The hematology assessments that are required weekly ( $\pm$  3 days) up to Week 26 and biweekly ( $\pm$  3 days) thereafter can be conducted at local laboratories or study sites, and will consist of the following procedures:

- Collect blood sample for hematology. Hematology results should be reviewed by the Investigator as soon as they are received from the laboratory;
- If a patient is receiving a blood transfusion during this visit or has received blood transfusions since the last visit (except for those patients who received an emergency transfusion), record the type of transfusion (simple, exchange, partial exchange), volume of blood that the patient received during the transfusions, and the mean hematocrit of the packed red blood cell units transfused (data obtained from the site's blood bank).

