#### 8.2.4.9 Adverse Event of Special Interest – Neutropenia (Definitions and Management)

##### **Definitions**

*Mild Neutropenia:* A confirmed ANC  $\geq 1.0 \times 10^9/L$  and  $< 1.5 \times 10^9/L$ .

*Moderate Neutropenia:* A confirmed ANC  $\geq 0.5 \times 10^9/L$  and  $< 1.0 \times 10^9/L$ .

*Severe Neutropenia/Agranulocytosis:* A confirmed ANC  $< 0.5 \times 10^9/L$ .

An absolute neutrophil count (ANC) is confirmed as being less than a specified value if two consecutive counts (maximum 3 days apart) are both less than the specified value. If both consecutive counts are below  $1.5 \times 10^9/L$  but not in the same severity category of neutropenia, a third count will be required to determine the severity.

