- Provide protective isolation; if clinically indicated, admit patient to hospital and obtain q4h vital signs.
- The Investigator will notify ApoPharma Inc. by fax.
- The Investigator will examine the patient the same day, if possible, including drug history and physical examination.
- If possible, obtain viral studies (CMV, parvovirus, hepatitis A/B/C), serum ALT, BUN, creatinine, and 10 mL serum split into two 5-mL aliquots for frozen storage, for future analysis.

Severe Neutropenia/Agranulocytosis (two consecutive Absolute Neutrophil Counts  $< 0.5 \times 10^9/L$ ):

Patients receiving deferiprone and who experience severe neutropenia/agranulocytosis (ANC  $< 0.5 \times 10^9/L$ ) will immediately discontinue treatment. The patients will be withdrawn from the study and will be followed daily until two successive ANCs are  $\geq 1.5 \times 10^9/L$ :

- The patient will be withdrawn from the study and monitored until resolution of the event.
- Provide protective isolation; if clinically indicated, admit patient to hospital and obtain q4h vital signs.
- The Investigator will notify ApoPharma Inc. by fax.
- The Investigator will examine the patient the same day, if possible, including drug history and physical examination.
- If possible, obtain viral studies (CMV, parvovirus, hepatitis A/B/C), serum ALT, BUN, creatinine, and 10 mL serum split into two 5-mL aliquots for frozen storage.
- Collect a blood sample to attempt to identify genetic or other biomarkers related to agranulocytosis (optional).
- If possible, obtain bone marrow aspirate for:
  - Histology
  - Progenitor culture
  - Frozen storage (1 mL sample)
- If possible, obtain bone marrow biopsy (minimum length 3 mm).
- Perform septic work-up including chest X-ray, blood, urine and throat cultures.
- Obtain q4h temperatures from patient (monitored by family at home if patient is not in the hospital).
- If warranted, administer granulocyte stimulating factors, such as G-CSF 10 µg/kg, as an inpatient if possible, beginning the same day that the ANC is confirmed as  $< 0.5 \times 10^9/L$ ; administer daily until ANC is  $> 1.5 \times 10^9/L$  on two consecutive days.
- If ANC  $< 0.5 \times 10^9/L$  for 7 days, repeat bone marrow biopsy and aspirate weekly during the period of agranulocytosis, if warranted.

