3.5 Schedule of Study Procedures

The efficacy and safety measurements/evaluations will be performed at visits outlined in Table 1 – Schedule of Study Procedures.

Table 1. Schedule of Study Procedures

STUDY PROCEDURE	Baseline Phase				Treatment Phase			
	Screening/ Baseline	Baseline	Hematology Assessments ¹	Telephone Calls (Week 1, 2, 3)	Monthly Visits (Week 4, 8, 16, 20, 32, 36, 44, 48)	Quarterly Visits (Week 12, 40)	Semi-Annual Visit (Week 26)	End of Study / Early Termination Visit ² (Week 52)
Informed Consent/Assent	X							
Eligibility Criteria	X							
Previous/current chelation therapy	X							
Confirmation of eligibility		X						
Demographic	X							
Randomization		X						
Medical history	X	V						R
Transfusion history	X	X						
Prior and Current medications	X	V						X
Hematology	X ³	X ⁴	X		X	X	X	X
Biochemistry	X ^{3,4}	V			X	X	X	X
Serum Pregnancy testing (females of childbearing potential only)	X ³	X			X	X	X	X
Urine Pregnancy testing (females of childbearing potential only)		X						
Serology	X ^{3,4}	V					X	X
Urinalysis	X ^{3,4}	V					X	X
Physical examination	X ^{3,4}	V					X	X
Vital signs (including weight and height) ⁵	X	X ⁴			X	X	X	X
12-lead ECG	X ^{3,4}	V					X	X
Blood sample for genetic polymorphism of agranulocytosis (optional)		X						

STUDY PROCEDURE	Baseline Phase			Treatment Phase				
	Screening/ Baseline	Baseline	Hematology Assessments ¹	Telephone Calls (Week 1, 2, 3)	Monthly Visits (Week 4, 8, 16, 20, 32, 36, 44, 48)	Quarterly Visits (Week 12, 40)	Semi-Annual Visit (Week 26)	End of Study / Early Termination Visit ² (Week 52)
Contraceptive counselling	X	X			X	X	X	
Quality of Life Questionnaire (SF-36/ Child Health Questionnaire)		X					X	X
Serum Ferritin		X				X	X	X
Liver MRI/LIC	X ^{4,6}						X	X
Cardiac MRI T2*	X ^{4,6}						X	X
Dose Calculation/Verify and adjust dose level		X			X	X	X	
Contact IVRS/IWRS		X			X	X	X	X
Dispense study medication		X			X	X	X	
Dispense Patient Diary Card		X			X	X	X	
Review and Collect Diary Card					X	X	X	X
Medical events/Adverse events	X	X		X	X	X	X	X
Concomitant medications				X	X	X	X	X
Transfusion information (if applicable) ⁷			X		X	X	X	X
Return used and unused study medication					X	X	X	X

X- To do, V- To verify, R- To review

1. Hematology testing is to be done weekly up to Week 26 and biweekly thereafter.
2. Early Termination: if patient withdraws from the study prior to Week 52, the patient must be seen for an early termination visit.

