14.3.6 Laboratory Data

14.3.6.1 Hematology

Table 14.3.6.1.1 Hemoglobin at each assessment

Table 14.3.6.1.2 Change in hemoglobin from baseline to each follow-up assessment

Table 14.3.6.1.3 Shift table for hemoglobin in abnormal range at baseline vs. last assessment: Feriprox group

Table 14.3.6.1.4 Shift table for hemoglobin in abnormal range at baseline vs. last assessment:

Deferoxamine group

Note: Similar tables will be produced for total white blood cell (WBC), absolute neutrophil count (ANC), and platelets.

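### The planned ANC tables can miss or understate neutrophil nadirs and never show confirmed neutropenia by the protocol's own grades

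*SAP*

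**What the plan says.** **Which counts are summarised.** SAP 8.5 rests all laboratory analyses on planned visits. It adds: "Laboratory data collected at unscheduled visits will be available in the data listings but not included in summary tables".

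**How shifts are built.** Values are classed as low, normal or high against the laboratory range, and "Shift tables comparing the distributions of these three categories at baseline versus end of treatment will be presented". The table list in SAP 14.3.6.1 names a slightly different end point: "Table 14.3.6.1.3 Shift table for hemoglobin in abnormal range at baseline vs. last assessment: Feriprox group". It extends the set to ANC: "Note: Similar tables will be produced for total white blood cell (WBC), absolute neutrophil count (ANC), and platelets".

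**When ANC is planned.** SAP 3.5, Table 1, footnote 1: "Hematology testing is to be done weekly up to Week 26 and biweekly thereafter". Protocol 5.4 allows ±3 days around each count and says these assessments "can be conducted at local laboratories or study sites".

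**How neutropenia is defined and followed.** Protocol 8.2.4.9 makes neutropenia the adverse event of special interest, with three grades: mild (1.0 to <1.5), moderate (0.5 to <1.0) and severe/agranulocytosis (<0.5), all × 10⁹/L. A count is confirmed below a threshold when "two consecutive counts (maximum 3 days apart) are both less than the specified value". If the two fall in different grades, a third count decides. Mild and moderate cases are then counted every 2 days. Severe cases are withdrawn and "will be followed daily until two successive ANCs are" at or above 1.5.

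**The concern.** Protocol 1.2 names agranulocytosis as the most significant serious event linked to deferiprone, and Protocol 11.2.3 lists ANC among the safety endpoints. The rule in SAP 8.5 removes from the summaries the very counts that the protocol uses to confirm, grade and follow this event. The shift table then looks at one late value per patient, so a fall and recovery between baseline and that value leaves no trace in it. No planned table uses the protocol's three grades: a count of 0.2 and a count just under the laboratory's lower limit are both simply low.

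What is at stake is the objective laboratory evidence on the main known risk. Without a graded worst-value table, a reader who wants the number of patients per arm with confirmed ANC below 0.5 must rebuild it from listings or rely on reported adverse event terms.

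**Working it through.** **1. The plan's own safety figures.** The chance of at least one event is 1 − (1 − p)ⁿ.

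| n | p | Computed | Stated |
|---|---|---|---|
| 300 | 2% | 99.77% | above 99% |
| 300 | 1% | 95.10% | above 95% |
| 213 | 2% | 98.65% | 98% |
| 213 | 1% | 88.24% | 88% |

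All are reproduced; none is in dispute.

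**2. Expected cases.** The inputs are 142 deferiprone patients at the interim (SAP, sample size text) and the rates in Protocol 1.2.

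- Agranulocytosis: 142 × 0.017 = 2.4. Chance of at least one: 1 − 0.983¹⁴² = 91.2%.
- Neutropenia: 142 × 0.062 = 8.8.
- Full planned arm of 200: 200 × 0.017 = 3.4 agranulocytosis cases (chance of at least one 96.8%).
- With the 17 ongoing patients added and a 2:1 split assumed: 230 × 2/3 = 153, and 153 × 0.017 = 2.6.

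**3. Can planned visits supply a confirming pair?** Shift each of two neighbouring visits by −3 to +3 days, giving 7 × 7 = 49 combinations. The gap is the nominal spacing plus the second shift minus the first.

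- Weekly: a gap of 3 days or less needs a difference in shifts of −4, −5 or −6, which arises in 3 + 2 + 1 = 6 of 49 combinations (12%). The smallest gap is 1 day.
- Two-weekly: the smallest gap is 14 − 6 = 8 days, so 0 of 49.

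This counts possibilities and does not claim that each is equally likely. It shows that confirmation under Protocol 8.2.4.9 almost always needs an unscheduled count, as do the counts every 2 days or daily that follow.

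**4. Would a low planned count exist at all?** The documents give no episode length, so take D days as an assumption. If onset falls at random between visits and planned counts continue, the chance that at least one planned count lands in the episode is min(1, D/7) for weekly and min(1, D/14) for two-weekly testing. Cases without one = 2.41 × (1 − that chance).

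| D (days) | Caught, weekly | Not caught, of 2.4 | Caught, two-weekly | Not caught, of 2.4 |
|---|---|---|---|---|
| 3 | 43% | 1.4 | 21% | 1.9 |
| 5 | 71% | 0.7 | 36% | 1.6 |
| 7 | 100% | 0 | 50% | 1.2 |
| 10 | 100% | 0 | 71% | 0.7 |
| 14 | 100% | 0 | 100% | 0 |

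Two qualifications apply. Protocol 1.2 puts the peak of agranulocytosis at 5 months, inside the weekly period, so the weekly columns matter more. In the other direction, a patient withdrawn after an unscheduled low count has only the Early Termination visit left, so planned counts do not continue as the formula assumes. A planned count that falls inside the episode also need not be the nadir.

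**5. What each planned output gives for ANC.**

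| Output | What it shows | What it leaves out |
|---|---|---|
| By-visit summary (SAP 17, hematology shells) | Mean, SD, minimum, maximum | Number of patients affected; unscheduled counts |
| Figure 14.3.1.2, repeated for ANC | Proportion abnormal per assessment | Grade; cumulative incidence per patient |
| Shift table | Low/normal/high at baseline and at the end | Nadir between those points; grade |
| AE tables (SAP 8.1) | Patients per preferred term, by severity, seriousness and relationship | Confirmed ANC grade |

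**6. An unsettled source.** The hematology shells cite listing 16.2.11, while local laboratory data sit in listing 16.2.31. The SAP does not say whether planned counts done locally enter the tables. If they do not, the gap is wider than step 4 suggests.

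**The case against.** The case on the other side is strong in several respects.

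- **Low planned counts do show.** With weekly and then two-weekly testing, many episodes will include one, and it enters the by-visit minimum and the proportion-abnormal figure. This stands. Neither output counts patients by grade.
- **The last value need not be a recovered one.** If unscheduled counts are excluded, so are most recovery counts. The Early Termination visit is due as soon as possible and within 1 month (Protocol 3.2), with no requirement to wait for recovery, and mild or moderate cases are withdrawn because ANC is still below 1.5 at 14 days. A still-low last value would appear in the shift table. This stands too: a recovered patient is classed by the later value, but not every patient will have recovered.
- **The adverse event route is open.** SAP 8.5 sends clinically significant values to the adverse event analysis whatever visit found them. SAP 8.1 tabulates terms by arm and lists serious events and withdrawals. This stands, with limits. Significance is the investigator's judgement in an open-label trial (Protocol 8.2.4.2). The severity scale merges CTCAE grades 3 to 5 (Protocol 8.2.4.5). The protocol's own adverse event table splits the signal into neutropenia 6.2%, agranulocytosis 1.7% and neutrophil count decreased 7.3%, and the SAP lists no table combining them.
- **The SAP does not depart from the protocol on shifts.** Protocol 11.4.1.4 plans the same comparison, and neither document promises a graded worst-value table. This stands, so the point is an improvement and not a correction of an error.
- **A worst-value table is not neutral.** The intensified counts in Protocol 4.6 and 8.2.4.9 are written mainly for patients on deferiprone. More counts give more chances of a low minimum, whereas a planned-visits rule treats the arms alike. This stands and shapes the fix.

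A reader might infer that confirmed neutropenia cannot appear in the ANC tables, that almost no case would show, or that the arms would look alike by construction. For the reasons above, the documents do not support any of these.

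**Conclusion.** The point holds as a limitation of the ANC summaries. Planned visits can rarely supply the protocol's confirming pair (6 of 49 weekly window combinations, 0 of 49 two-weekly). The tables can therefore miss or understate nadirs, and a patient who recovered is classed by a later value. None tabulates confirmed neutropenia by protocol grade. The events themselves remain visible in the adverse event and serious event outputs and in the listings.

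The size is small in number but concerns the key safety signal: of about 2.4 expected agranulocytosis cases among 142 deferiprone patients, 0 to 1.4 would lack a low planned count under weekly testing and 0 to 1.9 under two-weekly testing. This rests on an assumed episode length of 3 to 14 days, random onset, planned counts continuing through the episode, and the pooled 1.7% rate, which comes mainly from thalassemia patients (Protocol 1.4), carrying over to this population. The structural finding, that confirmed grades are not tabulated, needs none of these assumptions.

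**What to change.** Keep the existing tables and add to SAP 8.5, for ANC by arm:

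1. A shift from baseline to the worst post-baseline value over all planned, unscheduled, central and local counts, in the Protocol 8.2.4.9 classes (<0.5, 0.5 to <1.0, 1.0 to <1.5, ≥1.5 × 10⁹/L). State how long after the last dose counts are included.
2. The number of patients with confirmed neutropenia in each grade, by the protocol's two-count and third-count rules, and the time to first confirmed event.
3. The same worst-value table from planned visits only, placed beside the first. A note should say that intensified counts are written mainly for deferiprone patients, so the all-counts comparison has unequal ascertainment between arms.

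The SAP should also say whether local counts in listing 16.2.31 feed the hematology tables, and whether shifts end at end of treatment or at last assessment.

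This is a cheap improvement: one or two extra tables from data already collected, with no change to the primary analysis, data collection or patient management.

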### 4.3 Exclusion Criteria

Patients will be excluded from the study for **any** of the following reasons:

1. Thalassemia syndromes;
2. Myelodysplastic syndrome (MDS) or myelofibrosis;
3. Diamond Blackfan anemia;
4. Primary bone marrow failure;

5. Patients with a baseline LIC >30 mg/g dw (measured by MRI);
6. Unable or unwilling to undergo a 7-day washout period if currently being treated with deferiprone or deferoxamine or deferasirox;
7. Previous discontinuation of treatment with deferiprone or deferoxamine due to adverse events;
8. History or presence of hypersensitivity or idiosyncratic reaction to deferiprone or deferoxamine;
9. Treated with hydroxyurea within 30 days;
10. History of malignancy;
11. Evidence of abnormal liver function (serum ALT level(s) > 5 times upper limit of normal at screening or creatinine levels >2 times upper limit of normal at screening);
12. A serious, unstable illness, as judged by the Investigator, during the past 3 months before screening/baseline visit including but not limited to: hepatic, renal, gastro-enterologic, respiratory, cardiovascular, endocrinologic, neurologic or immunologic disease.
13. Clinically significant abnormal 12-lead ECG findings;
14. Cardiac MRI T2\* <10 ms
15. Myocardial infarction, cardiac arrest or cardiac failure within 1 year before screening/baseline visit;
16. Bowel disease causing malabsorption;
17. HIV positive patient;
18. Unable to undergo MRI;
19. Presence of metallic objects such as artificial joints, inner ear (cochlear) implants, brain aneurysm clips, pacemakers, and metallic foreign bodies in the eye or other body areas that would prevent use of MRI imaging;
20. History of alcohol or drug abuse;
21. Treatment with an investigational drug within 30 days or 5 half-lives (whichever is longer) preceding the first dose of study medication;
22. Participation in another clinical trial during the conduct of this study;
23. Pregnant, nursing females and females of childbearing potential who are sexually active and unwilling, or unable, to use an acceptable method of contraception;
24. Mental incapacity, unwillingness or language barriers precluding adequate understanding or co-operation;
25. Any condition that, in the opinion of the Investigators, would adversely affect ability to complete the study or its assessments.

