## 5.2 Screening/Baseline Visit (Day -60 to Day -1: Visit -1)

Assessment of eligibility:

The following procedures will take place at the Screening/Baseline visit:

- Explain the study to the patient and/or parent/legal representative, obtain written informed consent/assent, and give a copy to the patient and/or parent/legal representative;
- Assign the patient ID number (see [Section 4.8](#));
- Review previous/current chelation therapy;
- Record demographic information;
- Obtain medical history;
- Obtain transfusion history;
- Record prior and current medication(s);
- Collect blood sample for hematology, biochemistry (fasting glucose; patient must come to the site following a 10-hour fast), and serology (to be conducted within 14 days of starting study medication; will be considered as the baseline procedures for biochemistry);
- Collect blood sample for pregnancy testing for all females of childbearing potential. A negative result will be required for start of dosing;
- Collect urine for urinalysis;
- Perform physical examination (to be completed by Investigator or a qualified delegate);
- Take vital signs, weight, and height;
- Perform 12-lead ECG;
- If patient is identified as potentially eligible based on the available data (medical history, transfusional history, current medication(s), physical examination, vital signs), perform MRI scan for:

- Liver, and transmit to a central laboratory for interpretation and LIC calculation (to be conducted within two months prior to starting study drug; will be considered as the baseline procedure);
- Cardiac MRI T2\*, and transmit to a central laboratory for interpretation (to be conducted within two months prior to starting study drug; will be considered as the baseline procedure);
- Conduct contraceptive counselling for all sexually active patients;
- Review inclusion/exclusion criteria;
- Remind the patient, and/or if applicable patient's authorized legal representative, that she/he must carefully keep track of medical events and medication used to treat them;
- Instruct eligible patients to start washout of current chelation therapy (if required) 7 days prior to the baseline visit, and washout of hydroxyurea (if required) 30 days prior to the baseline visit;
- Schedule next study visit.

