8.1 Adverse Events

A summary table of adverse events will include the following information:

- number of patients exposed to study treatment
- number of patients experiencing at least one AE
- number of patients experiencing at least one severe AE
- number of patients experiencing at least one serious AE
- number of patients experiencing at least one drug-related AE
- number of deaths
- total number of patients withdrawn (and reason for withdrawal)
- number of withdrawals due to an AE

Adverse events will be coded using MedDRA. Adverse events are defined as AEs that occurred or worsened (increased in severity and/or frequency) on or after the first dose of study medication. Serious adverse events (SAEs) that occurred within 14 days after treatment discontinuation will be considered to be SAEs. Serious adverse events that occurred within 30 days after treatment discontinuation will be included in the database.

Adverse events will be summarized by treatment group using the total number of AEs and total exposure to the treatment, the total number and percent of patients who experience an AE, and the number and percent of patients who experienced an AE within each SOC (and preferred term within an SOC). AEs will also be presented by severity (mild, moderate, severe), by seriousness (serious, non-serious) and by relationship to study medication (at least possibly related, not related). The number of patients withdrawn will also be presented.

To count the number of patients who experienced each AE, patients who experienced the same AE multiple times will only be counted once for the corresponding preferred term. Similarly, if a patient experiences multiple AEs within the same SOC, that patient will be counted only once for that SOC. AEs will be tabulated presenting the SOC alphabetically, and within each SOC, preferred terms will be presented in decreasing order of the total number of patients who experienced each AE. In summaries presenting the

incidence of AEs by severity, seriousness, and relation to study medication, a patient with multiple events coded to a given preferred term or SOC will be counted once for that preferred term or SOC according to the most severe event, the most serious event, or the event with the closest relationship to study medication.

A listing of serious adverse events and a listing of withdrawals due to AEs will be presented. Patient deaths will be listed separately and discussed with patient narratives.

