14.3.6.2 Biochemistry

Table 14.3.6.2.1 Total protein at each assessment

Table 14.3.6.2.2 Change in total protein from baseline to each follow-up assessment

Table 14.3.6.2.3 Shift table for total protein in abnormal range at baseline vs. last assessment: Feriprox group

Table 14.3.6.2.4 Shift table for total protein in abnormal range at baseline vs. last assessment:

Deferoxamine group

Note: Similar tables will be produced for GGT, lactate dehydrogenase (LDH), sodium, potassium, chloride, glucose (fasting at screening visit only), total, direct and indirect bilirubin, AST, ALT, albumin; blood urea nitrogen, calcium, creatinine, uric acid, alkaline phosphatase, and amylase.

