14.3.2 Biochemistry

Figure 14.3.2.1 Mean line graph for total protein over visit

Figure 14.3.2.2 Proportion of patients with abnormal total protein at each assessment

Note: Similar tables will be produced for GGT, lactate dehydrogenase (LDH), sodium, potassium, chloride, glucose (fasting at screening visit only), total, direct and indirect bilirubin, AST, ALT, albumin; blood urea nitrogen, calcium, creatinine, uric acid, alkaline phosphatase, and amylase.

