Note: Similar tables will be produced for total white blood cell (WBC), absolute neutrophil count (ANC), and platelets.

Data source: 16.2.11 Listing of hematology

Table 14.3.6.1.3 Shift table for hemoglobin in abnormal range at baseline vs last assessment: Deferiprone group

		Last Assessment			P-value (McNemar's test)
	n (%)	Low	Normal	High	
Baseline	Low	xx (xx)	xx (xx)	xx (xx)	0.xxxx
	Normal	xx (xx)	xx (xx)	xx (xx)	
	High	xx (xx)	xx (xx)	xx (xx)	

Note: Similar tables will be produced for total white blood cell (WBC), absolute neutrophil count (ANC), and platelets.

Data source: 16.2.11 Listing of hematology

Table 14.3.6.1.4 Shift table for hemoglobin in abnormal range at baseline vs last assessment: Deferoxamine group

		Last Assessment			P-value (McNemar's test)
	n (%)	Low	Normal	High	
Baseline	Low	xx (xx)	xx (xx)	xx (xx)	0.xxxx
	Normal	xx (xx)	xx (xx)	xx (xx)	
	High	xx (xx)	xx (xx)	xx (xx)	

Note: Similar tables will be produced for total white blood cell (WBC), absolute neutrophil count (ANC), and platelets.

Data source: 16.2.11 Listing of hematology

Table 14.3.6.2.1 Total protein at each assessment

	Treatment				P-value (T-test)
	Hemoglobin	Deferiprone		Deferoxamine	
Visit	N	Mean ± SD (Min, Max)	N	Mean ± SD (Min, Max)	0xxxx
Baseline	xxx	xx.x ± xx.x (xx, xx)	xxx	xx.x ± xx.x (xx, xx)	0xxxx
Month 1	xxx	xx.x ± xx.x (xx, xx)	xxx	xx.x ± xx.x (xx, xx)	0xxxx
Month 2	xxx	xx.x ± xx.x (xx, xx)	xxx	xx.x ± xx.x (xx, xx)	0xxxx
Month 3	xxx	xx.x ± xx.x (xx, xx)	xxx	xx.x ± xx.x (xx, xx)	0xxxx
Month 4	xxx	xx.x ± xx.x (xx, xx)	xxx	xx.x ± xx.x (xx, xx)	0xxxx
...
Month 10	xxx	xx.x ± xx.x (xx, xx)	xxx	xx.x ± xx.x (xx, xx)	0xxxx
Month 11	xxx	xx.x ± xx.x (xx, xx)	xxx	xx.x ± xx.x (xx, xx)	0xxxx
Month 12	xxx	xx.x ± xx.x (xx, xx)	xxx	xx.x ± xx.x (xx, xx)	0xxxx

Note: Similar tables will be produced for GGT, lactate dehydrogenase (LDH), sodium, potassium, chloride, glucose (fasting at screening visit only), total, direct and indirect bilirubin, AST, ALT, albumin; blood urea nitrogen, calcium, creatinine, uric acid, alkaline phosphatase, and amylase.

Data source: 16.2.15 Listing of chemistry

Table 14.3.6.2.2 Change in total protein at each follow-up assessment

		Treatment			
Hemoglobin	Deferiprone		Deferoxamine		P-value (T-test)
Visit	N	Mean ± SD (Min, Max)	N	Mean ± SD (Min, Max)	0xxxx
Month 1	xxx	xx.x ± xx.x (xx, xx)	xxx	xx.x ± xx.x (xx, xx)	0xxxx
Month 2	xxx	xx.x ± xx.x (xx, xx)	xxx	xx.x ± xx.x (xx, xx)	0xxxx

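### No planned laboratory table or figure grades peak ALT or AST by arm; the shift table has one High class and compares baseline with the last assessment only

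*SAP*

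**What the plan says.** SAP 8.5 plans, for each chemistry test, descriptive statistics and change from baseline by scheduled visit, a three-way classification, and shift tables. In the classification, "laboratory test results will be categorized as low (< lower normal limit), normal (within normal range), and high (> upper normal limit"). On timing, the SAP table list (14.3.6.2) names a "Shift table for total protein in abnormal range at baseline vs. last assessment: Feriprox group", with a matching table for deferoxamine, and repeats the set for ALT and AST. On unscheduled results, SAP 8.5 says: "Laboratory data collected at unscheduled visits will be available in the data listings but not included in summary tables".

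Three other outputs bear on liver enzymes, and the first two are also repeated for ALT and AST:
- SAP figure 14.3.2.2: "Proportion of patients with abnormal total protein at each assessment".
- The by-visit shells in SAP 17, such as "Change in total protein at each follow-up assessment", with mean, SD, minimum and maximum by arm.
- SAP 8.1: "AEs will also be presented by severity (mild, moderate, severe"). Laboratory values judged clinically significant enter this route.

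At entry, Protocol 4.3 excludes "serum ALT level(s) > 5 times upper limit of normal at screening" and sets no numerical limit for AST. Protocol 5.2 says that the screening blood sample "will be considered as the baseline procedures for biochemistry".

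**The concern.** Comparing the safety of the two chelators is a secondary objective (Protocol 2.2). Protocol 1.2 lists raised ALT among the most common deferiprone adverse events, at 7.5% of patients in the sponsor's trials. Protocol 3.2 names liver-enzyme increases among reactions that may depend on dose. A reader of the safety report will want to know how many patients in each arm had a small, moderate or large peak.

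The one laboratory table that classifies patients cannot answer that, for two reasons. Patients may already be in its top class at entry. And it looks only at the end of follow-up, when a rise may have been treated by lowering or stopping the drug.

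**Working it through.** The plan states no figure on this point, so there is none to reproduce. The check sets the outputs side by side and follows the classification rule through.

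**1. What each output can show for ALT and AST**

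| Output | Time points | Size of rise | Patients counted by peak? |
|---|---|---|---|
| Shift table (SAP 8.5; 14.3.6.2.3 and .4) | Baseline and last assessment | One High class | No |
| By-visit value and change (14.3.6.2.1 and .2) | Each scheduled visit | Mean, SD, min, max | No |
| Figure 14.3.2.2 | Each assessment | Abnormal yes/no | No; visits are not linked |
| AE summaries (SAP 8.1) | Whole treatment period | Mild, moderate, severe | Partly; only rises entered as AEs |
| Chemistry listing (16.2.15) | All values | Actual value | No counts |

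**2. Patients who enter above the limit.** Screening ALT up to 5 times the limit is allowed, and that sample is the baseline.
- A rise from 2 to 10 times the limit is 10 / 2 = 5-fold. Both values are High, so the class does not change.
- A patient entering at 5 times the limit leaves the High class only after a fall of 1 − 1/5 = 80%. Any rise is invisible in the table.

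**3. Rises that resolve.** Protocol 8.2.2 schedules post-baseline biochemistry at weeks 4, 8, 12, 16, 20, 26, 32, 36, 40, 44, 48 and 52, which is 12 values. For a patient who completes, the shift table uses 1 of the 12 and leaves out 11. The last value may also follow corrective action: liver-enzyme increases are a ground for dose reduction, and Protocol 3.2 allows the early termination visit up to 1 month after treatment stops.

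**4. Unscheduled results.** These appear in listings only. Routine biochemistry is monthly and central, and I found no general scheme for extra liver tests. Protocol 8.2.4.9 does ask for ALT, if possible, in severe neutropenia and in moderate neutropenia that has not resolved by 14 days. Such a value misses the tables unless it falls on a planned visit. This limb probably touches few values.

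**5. Limits of the partial cover**
- A by-visit maximum describes one patient per visit and arm. With the interim arm sizes in the SAP, that is 1/142 = 0.7% of the deferiprone arm or 1/71 = 1.4% of the deferoxamine arm.
- Figure 14.3.2.2 does pick up transient rises at scheduled visits. It shows neither their size nor whether the same patients recur.
- AE severity merges CTCAE grades 3 to 5 into severe, and the grades themselves are not entered in the eCRF (Protocol 8.2.4.5). Entry depends on the investigator's view of clinical significance (Protocol 8.2.4.2) in an open-label trial. An abnormality belonging to a condition already recorded need not be entered separately. SAP 8.1 promises a presentation by severity, but the AE table list (14.3.1) names no such table; the overall summary counts only patients with any severe AE.

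**The case against.** The strongest reply is that the plan, taken whole, already covers liver safety. SAP 8.5 agrees with Protocol 11.4.1.4, which prescribes the same three classes, so there is no deviation. The protocol's adverse event of special interest is neutropenia, and nothing in the documents calls for classes by multiple of the limit. The AE route counts each patient once per preferred term at the worst severity, recommends CTCAE as the guide, and is not tied to scheduled visits. A rise from 2 to 10 times the limit would push up that visit's maximum, appear in the listing, and very likely be recorded as an AE. The values are kept, and the SAP allows further tables to be added.

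Much of this stands. A reader might infer that the plan would miss a liver signal altogether, or that transient rises go unseen. The documents support neither: both limits belong to the shift table, and other outputs look at every visit. On entry, AST has no numerical limit, but exclusions 12 and 25 let the investigator keep out patients with unstable hepatic disease.

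What the reply does not supply is a count, by arm, of patients by size of measured peak. The AE route comes nearest, but it rests on judgement and has one class for everything from grade 3 upward. Adding the table later is possible, but cut-points chosen after seeing open-label data carry less weight.

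**Conclusion.** The point holds as a limited gap in the safety summaries. No planned laboratory table or figure grades peak ALT or AST by arm, and the shift table cannot show worsening from an elevated baseline or rises that resolve before the last assessment. Maximum by visit, proportion abnormal by visit, and AE severity cover part of this.

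The number of patients affected cannot be computed: the documents give neither the share entering above the limit nor the distribution of rises. A reader might apply the 7.5% rate to the interim arm (0.075 × 142 = 10.65, about 11 patients) and take that as the number affected. That is not supported. The rate describes reported events in earlier trials with mainly thalassemia patients, says nothing about size of rise, and concerns events that would reach the AE tables.

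No efficacy conclusion, alpha level or power figure changes. The conclusion rests on reading the table list, figure list and shells as the planned set. The change is a worthwhile, inexpensive improvement to a stated safety comparison.

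**What to change.** Keep the three-class shift table, since the protocol prescribes it. Add to SAP 8.5, for ALT and AST separately and by arm:
- the number and percent of patients whose highest post-baseline value exceeds 3, 5 and 10 times the upper limit, cross-tabulated by baseline class (up to 1, above 1 to 3, above 3 to 5 times the limit, and above 5 for AST);
- for patients above the limit at baseline, the number whose highest value exceeds 2 and 3 times their own baseline;
- unscheduled values in the maximum wherever a reference limit is available, with a count of those left out because none was.

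The cut-points are a proposal; the sponsor may choose others if they are fixed before the analysis.

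The cost is one paragraph and one extra descriptive table per enzyme. Scheduled values are central-laboratory data already collected, so that part needs no new data and no protocol change. The documents do not say whether limits are held for unscheduled values, so that part is conditional.
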